- **The proportion of people with treatment failure over 6 months and 12 months**, a binary outcome, will be modeled using log binomial models to report relative risks. We will use the randomization group as a predictor. Clustered log-binomial regression will then be used to estimate the same regression model.
- **A decision tree model-based cost-effectiveness analysis will be conducted to assess adalimumab therapy.** The cost-effectiveness analysis will be conducted separately for the US, UK, and Australia. Healthcare costs will be gathered from appropriate US, UK, and Australia sources under the perspective of a third-party payer. In the US, costs will be estimated from the Medicare Physician Reimbursement Rates and the Red Book average wholesale prices. In the UK, costs will be estimated from the National Health System (NHS) reference costs published by the Department of Health. In Australia, costs will be estimated from the Medicare Benefits Scheme (MBS) reference costs. Each item will be multiplied by the unit cost associated with the item. We will consider the following

costs: (1) doctor visits, (2) procedural costs (e.g., OCT scans, laboratory tests, etc.), and (3) medications. Total costs per patients will be summarized in 2019 USD. Protocol-induced costs will not be included in the total patient costs as these are imposed by the trial protocol. We will use the following two measures of effectiveness: (1) time to inflammation recurrence during the 12-month study period and (2) gain in quality-adjusted life years (QALYs) over 12 months. Time to inflammation, or time to treatment failure, is defined in Section 2.3. The EQ-5D-Y from baseline, month 6, and month 12 will be used to calculate utility values ranging from 0 (equivalent to being dead) to 1 (perfect health). We will calculate the number of QALYs gained for each patient by estimating the area under the curve (AUC) using the three utility value estimates (e.g., baseline, month 6, and month 12).

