We will use the TreeAge Pro software to develop our decision tree model. Our model will contain one decision node to stop or continue adalimumab. To calculate the incremental cost effectiveness ratio (ICER) we will divide the mean difference in patient costs between stopping and continuing adalimumab by the mean difference in effects.^{16,17} As costs will be different for our three enrollment countries we will create separate decision tree models. The ICERs will be interpreted as the following: (1) the costs per inflammation-free years and (2) the costs per QALY gained. Non-parametric bootstrap statistical methods will be used to calculate confidence intervals and derive a cost-effectiveness acceptability curve.

Planned Secondary Analyses with Alternative Outcomes

The following additional analyses provide further information about the disposition of study subjects. In reporting, these will be sharply distinguished from the primary outcome. We propose to report 95% confidence intervals for estimates pertinent to the analyses described below. Note, these are of less scientific importance than the primary outcome analyses, but are included because of scientific interest.

- **The BCVA**, a continuous outcome, will be modeled using a linear regression model. Analyses will be conducted with BCVA represented as logMAR. A linear regression model for the actual BCVA at month 6 and 12 will be fitted, adjusting for baseline BCVA. The model will include fixed effects for country and baseline antimetabolite use, following the stratified randomization. The following will serve as a template for analyzing other continuous variables. Only eyes affected with uveitis will be included in all the vision analyses.

The rationale for further longitudinal analysis is that patients who fail or experience flares may exhibit decreased visual acuity. Such inferences may be complicated by the fact that following failure and the consequent cessation of trial protocol, pertinent values of the visual acuity are no longer available. Analysis of available data only is expected to yield biased inference, and we propose to avoid

conditioning on post-randomization covariates.

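### The cost-per-QALY ratio uses an unadjusted difference in area under the utility curve, so it loses precision and carries part of any chance baseline EQ-5D-Y gap into its denominator

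*SAP*

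**What the plan says.** The cost-effectiveness analysis is among the planned secondary analyses of Specific Aim 1 (SAP 3.1.1). It has two effect measures: time to recurrence of inflammation, and "gain in quality-adjusted life years (QALYs) over 12 months". For the second, "The EQ-5D-Y from baseline, month 6, and month 12 will be used to calculate utility values", and the QALY for each patient is the area through those three values: "We will calculate the number of QALYs gained for each patient by estimating the area under the curve (AUC) using the three utility value". For the ratio, "we will divide the mean difference in patient costs between stopping and continuing adalimumab by the mean difference in effects". Uncertainty is handled by resampling: "Non-parametric bootstrap statistical methods will be used to calculate confidence intervals". The SAP also states that "The cost-effectiveness analysis will be conducted separately for the US, UK, and Australia", and gives differing costs as the reason for separate decision trees. It does not say whether the health effects are pooled or also estimated within each country.

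No regression and no baseline covariate is named for the QALY difference. In the same section, the template for continuous outcomes does adjust: "A linear regression model for the actual BCVA at month 6 and 12 will be fitted, adjusting for baseline BCVA". That template is extended to final values of a list of outcomes which includes the EQ-5D-Y score, but not QALYs.

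**The concern.** Baseline utility is measured before treatment can act, yet it is one of the three points that define the area. It enters the QALY directly, and again through its correlation with the month 6 and month 12 values. Part of any chance difference between arms at baseline is therefore counted as an effect of stopping or continuing adalimumab, in the denominator of a ratio. If the true incremental QALY over one year is small, which is plausible but not a figure the SAP gives, a shift of this kind could matter to the size or even the sign of the ratio. An unadjusted comparison also leaves in variance that a value already collected would remove. Cost-effectiveness is a named secondary objective (SAP 2.3.1), and financial burden is part of the study rationale (Protocol 2.1).

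**Working it through.** The SAP gives no expected QALY or cost-effectiveness figure, so there is none to reproduce. The check derives how a baseline gap propagates and what adjustment would gain.

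**Inputs from the documents**
- Utilities at baseline, month 6 and month 12 (SAP 3.1.1).
- 59 patients per arm and 10% loss to follow-up (SAP 3.3.1): 59 × 0.9 ≈ 53 per arm.
- Expected country split of 51%, 43% and 6% (Protocol 5.5). Of 118 patients at 1:1, that is 118 × 0.51 / 2 = 30.1 per arm (US), 25.4 (UK) and 3.5 (Australia), before losses.

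**Assumptions**
- Trapezoid rule with equal spacing.
- Equal variance at the three visits and a common correlation r between visits, taken as 0.3 to 0.7.
- Utility SD of 0.10 to 0.25. The value 0.173 is the 17.3 points in SAP 3.3.2.1 divided by 100. The documents do not establish that this is the SD of a 0–1 utility, so it is illustrative only.

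**Step 1: weights.** QALY = 0.5(u0 + u6)/2 + 0.5(u6 + u12)/2 = 0.25u0 + 0.50u6 + 0.25u12.

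**Step 2: carry-through.** A baseline gap d shifts the expected QALY difference by 0.25d + 0.50rd + 0.25rd = (0.25 + 0.75r)d.

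**Step 3: variance per patient, in units of SD².** Unadjusted: 0.375 + 0.625r. Adjusted for baseline: that minus (0.25 + 0.75r)².

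| r | Carry-through | Unadjusted variance | Adjusted variance | Reduction |
|---|---|---|---|---|
| 0.3 | 0.475 | 0.5625 | 0.3369 | 40% |
| 0.5 | 0.625 | 0.6875 | 0.2969 | 57% |
| 0.7 | 0.775 | 0.8125 | 0.2119 | 74% |

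The SD cancels from the percentage reduction. At SD 0.173, r = 0.5 and 53 per arm, the standard error of the QALY difference falls from 0.0279 to 0.0183.

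**Step 4: shift from a one-standard-error baseline gap at r = 0.5.** Shift = 0.625 × SD × √(2/n).

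| Setting | n per arm | SD | One-SE gap | Shift in QALY difference |
|---|---|---|---|---|
| Pooled | 53 | 0.10 | 0.019 | 0.012 |
| Pooled | 53 | 0.173 | 0.034 | 0.021 |
| Pooled | 53 | 0.25 | 0.049 | 0.030 |
| US only | 30.1 | 0.173 | 0.045 | 0.028 |
| UK only | 25.4 | 0.173 | 0.049 | 0.030 |
| Australia only | 3.5 | 0.173 | 0.130 | 0.081 |

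**Step 5: simulation.** In 6,000 simulated trials with no treatment effect (53 per arm, SD 0.173), the slope of the unadjusted QALY difference on the baseline gap was 0.478, 0.625 and 0.776 for r = 0.3, 0.5 and 0.7. With baseline utility in the regression it was 0.005 or less. At r = 0.5 the simulated standard error fell from 0.0282 to 0.0186, slightly above the formula value because the baseline slope must be estimated.

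**The case against.** The strongest reply is that allocation is randomized 1:1 and stratified, so the unadjusted difference is unbiased on average, and that the bootstrap already reflects sampling variation from chance imbalance. This stands. A reader might infer that the planned ratio rests on a biased estimate, or that a baseline gap passes into it in full. The documents support neither: the carry-through is partial (about 0.48 to 0.78 for r = 0.3 to 0.7), and what is lost is precision and balance conditional on the observed baseline. The bootstrap describes the spread but does not remove an imbalance that has occurred.

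A second reply is that QALYs gained could mean area net of baseline utility. The SAP does not say so, and that version would over-correct: its carry-through is −0.75(1 − r), or −0.375 at r = 0.5. Its variance at r = 0.5 is 0.4375 SD², against 0.2969 with regression.

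A third is that a mean difference in effects could be a regression-adjusted one. The wording does not exclude this, but neither does it specify it, and no covariate is named.

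A fourth concerns reach, and it stands. Only one of the two ratios uses utilities. Analyses after each aim's primary analysis are descriptive (SAP 3.5). It would also be wrong to infer that the instrument is nowhere baseline-adjusted, since the EQ-5D-Y score follows the adjusted template. The gap is confined to its use in QALYs.

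**Conclusion.** The point holds for the cost-per-QALY ratio only. The cost per inflammation-free year and the primary Cox analysis are untouched. As written, the plan gives up about 40% to 74% of the variance of the QALY difference for r = 0.3 to 0.7, a result that needs equal variances and a common correlation but no SD. It also lets about half to three quarters of a chance baseline gap through. In absolute terms, a one-standard-error gap is worth about 0.012 to 0.030 QALY pooled (r = 0.5, SD 0.10 to 0.25), or about 0.028, 0.030 and 0.081 for the US, UK and Australia if effects are estimated by country (r = 0.5, SD 0.173). The SDs and correlations are assumptions. The patient numbers are planned ones and may be high: EQ-5D-Y is completed from age 4 while enrollment starts at age 2, and enrollment stopped early. Whether such shifts would change the sign of the ratio cannot be judged, because the documents give no expected incremental QALY.

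**What to change.** In SAP 3.1.1, specify that the incremental QALY is the randomization-group coefficient from a regression of each patient's QALY on group, baseline EQ-5D-Y utility and baseline antimetabolite use. Repeat that regression in every bootstrap replicate used for the interval and the acceptability curve.

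State whether effects are pooled or country-specific. Include country as a covariate only where effects are pooled, since it is constant within a single country. Do not fit a separate adjusted model in Australia: about 7 patients (118 × 0.06) and 4 coefficients leave 3 residual degrees of freedom, and many bootstrap replicates would be unstable or singular. Apply the pooled adjusted QALY effect with Australian costs instead.

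SAP version 5 was written after the interim analysis and unmasking (SAP 12). The change should therefore be labelled as post-unmasking, as was done for the February 2024 additions, and the unadjusted result reported beside it. Baseline EQ-5D-Y is already collected (Protocol 1.3), so no new data are needed. The downside is one or two extra parameters, and more where country is included.

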We propose imputation of post-failure BCVA by *last observation carried forward* (LOCF), followed by pooled regression (clustered robust standard errors on individual). We propose to do so only when BCVA is available at the time (study visit) at which treatment failure is declared. We will use all BCVA measurements until either treatment failure or completion of the trial and report the coefficient for randomization group, adjusting for baseline antimetabolite use and country.

We also propose to descriptively report mean, median BCVA (together with standard deviation and interquartile range) of patients at each visit. Actual BCVA will be reported in a descriptive analysis.

This collection of procedures serves as a template for all continuous outcomes for which we assess final values (below).

In Aim 3, these regression models will be examined on an intent to treat basis, so time/outcomes after treatment failure are included in the analyses.

The following regression analyses will be conducted following the templates above: statistical predictor will be randomization group, and we include fixed effects for baseline antimetabolite and country. A separate model will include country by treatment interaction. Treatment effects will be only reported by stratum when heterogeneity or interactions are found.

Final values of the following continuous outcome variables will be modeled following the template found above in this Planned Secondary Analyses with Alternative Outcomes section:

- **The CHAQ score**
 - For this quality-of-life measurement and the three specified immediately below, a separate analysis comparing the patient's baseline value with their value at the time of failure, 6 and 12 months will be considered.
- **The EQ-5D-Y score**
- **The CVFQ score**
- **The EYE-Q score**
- **The JADAS-10 and JADAS-27 scores**
- **Estimated ADA levels**

Final values of the following binary outcome variables will be modeled with log binomial regression following the similar template in the Planned Subsidiary Analyses of the Primary Model section:

- **The proportion of patients who exhibit one or more arthritis flares**
- **The proportion of patients who achieve an improvement in JADAS-10**
- **The proportion exhibiting macular edema**

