Finally, we propose to measure patients' perceived treatment allocation to assess the effectiveness of patient masking to their allocation. We will measure patients' perceived treatment group before unmasking at either the time of treatment failure or at 12 months (the primary endpoint) if the patient does not experience treatment failure. We test for differences between groups using a Fisher's exact test for differences in a categorical outcome (adalimumab, placebo, don't know) stratified by whether the patient had treatment failure. Stratification is necessary to prevent bias in the event that the treatment group influences treatment failure, which in turn influences the patient's guess.

Analysis of secondary outcomes following the interim: Given the DSMC's decision on February 14, 2024 to stop enrollment based on interim efficacy, the investigator team decided to publish the interim analysis of the primary outcome immediately, without waiting for enrolled patients to complete their 12-month follow-up. To provide timely information for key secondary outcomes at the interim point in the trial given incomplete follow-up of longitudinal outcomes on many patients, we propose the following analyses that use all available information at the time of the interim. We propose to include longitudinal measures of four secondary outcomes measured through 12 months, treatment failure or censoring (whichever occurs first): BCVA, JADAS scores, adalimumab drug levels, and adalimumab antibody levels. The analysis of each outcome will follow the same general method. A longitudinal, linear mixed model will be fit, including fixed effects for stratification variables (antimetabolite use, country), treatment assignment, and the baseline measure of the outcome. A random effect for patient will account for repeated outcome measures. This is identical to the planned analyses above, but includes all available longitudinal measures (not only those at the primary endpoint or censoring at 6- or 12-months). These new analyses were specified in February 2024, after knowledge of the primary analysis and interim stopping.

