3.3.2 Power for Subgroup Analyses and Other Analyses

Our primary analysis is powered at 88% and most secondary analyses are reported at 80% power.

3.3.2.1 Specific Aim 1

Planned Secondary Analyses

- **Time to treatment failure, with censoring at 6 months.** We anticipate 80% power to detect a hazard ratio of 2.0 between randomization groups, based on 118 subjects (we anticipate same loss to follow up of 10%).
- **The proportion of people with uveitis flares over 6 months.** For sample size planning, we assume a test of proportions between the two randomization groups. Based on prior research, we expect 70% of those who discontinue adalimumab to experience flare by 6 months.²⁴ We anticipate 80% power to detect a difference of 28% between the groups, based on 118 subjects. Note that we anticipate fewer flares in the continuation group, but the test will be two-sided at alpha of 5%.
- **The proportion of people with uveitis flares over 12 months.** Based on prior research, we expect about 80% of those who discontinue adalimumab will have a uveitis flare by 12 months.²⁴ With our total sample size of 118 and the assumed 10% loss to follow-up by 12 months, with 80% power, we anticipate a power to detect a difference of 28% in the flare rate between the groups.

Planned Secondary Analyses with Alternative Outcomes

- **Longitudinal BCVA.** For sample size assessment, we assume a T-test comparing change scores between the two randomization groups. We assume a standard deviation of 0.59, based on prior research.²⁹ The total sample size of 118 and the assumed 10% loss to follow-up by 12 months provides 80% power to detect a difference of 0.32 logMar.
- **The CHAQ score.** For sample size planning, we assume a T-test comparing change scores between the two randomization groups. We shall assume a standard deviation of 23 based on prior research.³⁰ Thus with the total sample size of 118 and the assumed 10% loss to follow-up by 12 months, with 80% power we can detect a difference of approximately 13 points.
- **The EQ-5D-Y score.** For sample size planning, we assume a T-test comparing change scores between randomization groups. Assuming a standard deviation of 17.3,³¹ the total sample size of 118 and assumed 10% loss to follow-up by 12 months provides over 80% power to detect a mean difference of 7.9 points.

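### The pooled longitudinal BCVA regression, one part of the template for the other continuous outcomes, does not list the baseline value as a covariate and does not restrict outcome rows to post-baseline visits

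*SAP*

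**What the plan says.** SAP section 3.1.1 (Planned Secondary Analyses with Alternative Outcomes) sets out two regressions for BCVA.

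- **Month 6/12 regression.** "A linear regression model for the actual BCVA at month 6 and 12 will be fitted, adjusting for baseline BCVA", with country and antimetabolite use as fixed effects.
- **Pooled longitudinal regression.** BCVA after failure is imputed by last observation carried forward (LOCF), then a pooled regression with patient-clustered robust standard errors is fitted. On the data: "We will use all BCVA measurements until either treatment failure or completion of the trial and report the coefficient for randomization group". On the model: "report the coefficient for randomization group, adjusting for baseline antimetabolite use and country".

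The SAP then says "This collection of procedures serves as a template for all continuous outcomes for which we assess final values (below"). The text introducing the other outcomes names randomization group, antimetabolite use and country, again without the outcome's baseline value.

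Two other places bear on this. The mixed model added in February 2024 for BCVA, JADAS, drug levels and antibody levels includes fixed effects for the stratification variables, "treatment assignment, and the baseline measure of the outcome". The SAP describes that model as identical to the planned analyses except that it uses all longitudinal measures. SAP section 3.3.2.1, on power for longitudinal BCVA, states "we assume a T-test comparing change scores between the two randomization groups".

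**The concern.** Visual acuity differs far more between patients than most treatments change it, and the baseline value is the obvious covariate for removing that variation. It is already collected. A pooled model without it carries the full between-patient variance into the treatment contrast, and any chance baseline difference between arms goes straight into the coefficient.

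Separately, BCVA is measured at the baseline visit (Protocol section 1.3), and a literal reading of the row definition includes it. Treatment cannot affect that value, so including it pulls the estimated effect toward zero.

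The SAP reports these results as estimates with 95% confidence intervals, so interval width and coefficient size are what readers will see. The descriptions also disagree with one another after unmasking, which leaves the choice of model to the analyst.

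**Working it through.** **1. The plan's own figure.** Inputs from SAP section 3.3.2.1: 118 patients, 10% loss, SD 0.59, difference 0.32 logMAR. Two-sided alpha 0.05 is taken from section 3.3.1. Retained: 118 × 0.9 = 106, or 53 per arm. Standard error = 0.59 × √(2/53) = 0.1146; 0.32/0.1146 = 2.79; 2.79 − 1.96 = 0.83; power = 79.7% (79.0% by noncentral t). The stated 80% reproduces for a t-test on change scores. That test uses baseline; the pooled regression as listed does not.

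**2. The four descriptions side by side.**

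| Place in SAP | Baseline used? | Post-baseline rows only? |
|---|---|---|
| 3.1.1, Month 6/12 regression | Yes, covariate | Yes, by definition |
| 3.1.1, pooled longitudinal regression | Not listed | Not stated |
| 3.1.1, post-interim mixed model | Yes, covariate | Not stated, but implied by the covariate |
| 3.3.2.1, BCVA power | Yes, change score | Yes, by definition |

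**3. Precision lost by omitting the baseline covariate.** Assume equal correlation ρ between any two measurements on a patient, and k post-baseline visits. In units of the single-measurement variance, the variance of a patient's follow-up mean is:

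- unadjusted: (1 + (k−1)ρ)/k
- adjusted for baseline: (1 + (k−1)ρ)/k − ρ²

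The SD cancels in the ratio. For BCVA, k = 8 (Months 1–4, 6, 8, 10, 12). Example at ρ = 0.6: unadjusted 5.2/8 = 0.650; adjusted 0.650 − 0.360 = 0.290; standard-error ratio √(0.650/0.290) = 1.50.

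The documents give no ρ, so the full range is shown. The LOCF column is a simulation: 118 patients, exponential failure with medians of 10 and 20 weeks (section 3.3.1), dropout 0.0022 per week (SAP appendix 13.1), cluster-robust standard errors, 400 replicates. It assumes a constant treatment effect and failure unrelated to BCVA, and leaves out the stratification covariates.

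| ρ (assumed) | 8 complete visits, formula | 8 visits, LOCF, simulated | 2 follow-up visits, formula |
|---|---|---|---|
| 0.3 | 1.14 | 1.07 | 1.08 |
| 0.5 | 1.34 | 1.22 | 1.22 |
| 0.6 | 1.50 | 1.35 | 1.35 |
| 0.7 | 1.73 | 1.53 | 1.54 |
| 0.8 | 2.11 | 1.85 | 1.86 |
| 0.9 | 2.98 | 2.57 | 2.60 |

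The two-visit column corresponds to the questionnaires, scheduled at Months 6 and 12 (Protocol section 8.1).

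**4. Effect of counting baseline as an outcome row.** With a constant post-baseline effect, the pooled coefficient is multiplied by k/(k+1). For BCVA this is 8/9 = 0.89, an 11% shrinkage; the LOCF simulation gave about the same. The SAP asks for LOCF but also describes measurements up to failure. If rows stop at failure, patients contribute fewer follow-up rows, and the simulated shrinkage at the planned failure times is about 23%.

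The raw standard error does not rise. The variance becomes (1 + kρ)/(k+1); at ρ = 0.6 that is 5.8/9 = 0.644, against 0.650 without the baseline row.

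**5. Why no absolute detectable differences are given.** Section 3.3.2.1 states SD 0.59 directly after assuming change scores and does not say whether it describes single values or changes. Under equal correlation, the change-score SD is √(2(1−ρ)) times the single-value SD, so the two readings coincide only at ρ = 0.5. The ratios above do not depend on this.

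**The case against.** The strongest reply is that the SAP's intent is baseline adjustment throughout. The template is a collection of procedures that begins with a baseline-adjusted regression, and section 3.1.2 says the emphasis was on final values. The February 2024 model includes baseline and is called identical to what was planned. A baseline-adjusted BCVA estimate will therefore be reported in any case. For the four questionnaires, the SAP also says it will consider comparing each patient's baseline with later values.

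Much of this stands. A reader might infer that the whole template ignores baseline; it does not. It is also unclear whether the pooled model carries over to the other outcomes: section 2.3.1 calls those comparisons longitudinal, while section 3.1.1 speaks of their final values. For BCVA, JADAS and antibody levels, the post-interim model supplies a baseline-adjusted longitudinal analysis.

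A reader might also infer that standard errors are 1.5 to 3 times too large. That needs ρ of about 0.6 to 0.9 and eight complete visits, and the documents support neither. With LOCF at the planned failure times, 1.5 needs ρ of about 0.7, and 3 is not reached at 0.9. Nor is a shortfall against the stated BCVA power shown, given the unclear SD.

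Under randomization, chance baseline imbalance costs precision and does not bias the estimator.

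None of this supplies the missing words. The pooled regression still lists no baseline value and sets no starting visit. The claim that the later model is identical to the plan does not fit that covariate list. The post-interim model does not cover CHAQ, EQ-5D-Y, CVFQ or EYE-Q, and the baseline comparison mentioned for those is not a between-arm longitudinal model.

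**Conclusion.** The concern holds as a minor specification gap with two distinct consequences.

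- **Precision.** Omitting baseline makes the standard error about 1.1 to 3.0 times that of the adjusted model for assumed correlations of 0.3 to 0.9 with complete visits, or about 1.1 to 2.6 times with LOCF at the planned failure times. The ratio exceeds 1 throughout, but its size depends on a correlation the documents do not give.
- **Attenuation.** If baseline rows are counted, the BCVA coefficient shrinks by about 11% (LOCF or complete visits) or about 23% (rows ending at failure). This is conditional on a literal reading of the row definition. It is not a cause of larger standard errors.

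The reach is the pooled longitudinal model for BCVA and any outcome that inherits it, most clearly the four questionnaires. SAP section 3.5 makes analyses after each Aim's primary descriptive, and section 3.1.1 ranks these below the primary outcome analyses. The primary Cox analysis does not use this model.

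**What to change.** In the pooled longitudinal paragraph of SAP section 3.1.1, state that outcome rows are post-baseline measurements only, and that the regression adjusts for the baseline value of the outcome together with antimetabolite use and country. Say that this applies to every outcome using the template. Then reconcile the Month 6/12 regression, the pooled regression and the post-interim mixed model, so that the statement that the last is identical to the plan is true or is withdrawn.

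No new data are needed. The cost is procedural: SAP version 5 already postdates the interim analysis and unmasking, so the edit must be dated and labelled as a post-unmasking change to secondary, descriptive analyses, as the February 2024 additions were.
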